**Table 8-1 Part A: Assessment schedule**

Visit Name	S1 [6]	V1		V2	V3	V4	V5	V6	V7	V8	V9
Study Day	-3 to -1	1		3	5	8 ± 2	15 ± 3	22 ± 4	29 ± 5 (EOS) [7]	61 ± 5	EOS[8] / 91 ±7
		pre-dose	post-dose								
STUDY ENTRY AND GENERAL ASSESSMENTS											
Informed consent	(X)	X									
Inclusion/Exclusion criteria	(X)	X									
Demographics	(X)	X									
Complete medical history	(X)	X									
INVESTIGATIONAL PRODUCT											
Ensovibep (MP0420)/Placebo			X								
SAFETY ASSESSMENTS											
Prior/concomitant medication evaluation	Continuous starting after ICF signature, until 3 months after study medication										
Prior/concomitant hospitalization and procedures	Continuous starting after ICF signature, until 3 months after study medication										
AE evaluation	Continuous starting after ICF signature, until 3 months after study medication										
Local tolerability			X								
Physical examination and vital signs [1]	(X)	X									
General physical appearance and vital signs [1]				X	X	X	X		X		X
Body temperature, respiratory rate, oximetry	(X)	X		X	X	X	X		X		X

Visit Name	S1 [6]	V1		V2	V3	V4	V5	V6	V7	V8	V9
Study Day	-3 to -1	1		3	5	8 ± 2	15 ± 3	22 ± 4	29 ± 5 (EOS) [7]	61 ± 5	EOS[8] / 91 ±7
		pre-dose	post-dose								
Weight	(X)	X									X
Height	(X)	X									
Hematology, chemistry and coagulation safety tests		X		X			X		X	X	X
Pregnancy test in WOCBP [2]	(X)	X									X
Birth Control	Continuous until EOS [3]										
	VIROLOGY & SEROLOGY ASSESSMENTS										
Rapid SARS-CoV-2 antigen test	(X)	X									
SARS-CoV-2 sample (quantitative RT-PCR, mutation analysis)		X		X	X	X	X		X		X
PK blood sample		X	XX [4]	X		X	X		X	X	X
Blood sample for serum biomarkers		X		X		X	X		X		X
	CLINICAL ASSESSMENTS										
Symptom score [5]		X		Daily assessment				X	X		

Visit Name	S1 [6]	V1		V2	V3	V4	V5	V6	V7	V8	V9
Study Day	-3 to -1	1		3	5	8 ± 2	15 ± 3	22 ± 4	29 ± 5 (EOS) [7]	61 ± 5	EOS[8] / 91 ±7
		pre-dose	post-dose								

[REDACTED]; AE=adverse event; EOS=end-of-study; FDA=Food and Drug Administration; ICF=informed consent form; PCR=polymerase chain reaction; PK=pharmacokinetics; PRO=patient-reported outcome; RT=reverse transcriptase; S=screening; [REDACTED]; V=visit; WOCBP=women of child-bearing potential.

1. Vital signs consist of systolic and diastolic blood pressure and heart rate.

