## 10.2 Additional safety monitoring

### 10.2.1 Liver safety monitoring

To ensure patient safety and enhance reliability in determining the hepatotoxic potential of an investigational drug, a standardized process for identification, monitoring and evaluation of liver events has to be followed.

Please refer to [Table 16-1](#), [Table 16-2](#), and [Table 16-3](#) in [Appendix 16](#) for complete definitions of liver laboratory triggers.

Once a patient is exposed to study treatment, every liver event defined in [Table 16-1](#) should be followed up by the investigator or designated personnel at the trial site, as summarized below. Additional details on actions required in case of liver events are outlined in [Table 16-2](#). Repeat liver chemistry tests (i.e., alanine aminotransferase [ALT], aspartate aminotransferase [AST], total bilirubin [TBL], prothrombin time [PT]/international normalized ratio [INR], alkaline phosphatase [ALP] and gamma-glutamyl transferase [G-GT]) to confirm elevation.

- These liver chemistry repeats will be performed using the central laboratory. If results will not be available from the central laboratory, then the repeats can also be performed at a local laboratory to monitor the safety of the patient. If a liver event is subsequently reported, any local liver chemistry tests previously conducted that are associated with this event should be recorded as part of the liver AE.
  - If the initial elevation is confirmed, close observation of the patient will be initiated
  - Hospitalization of the patient if appropriate
  - Causality assessment of the liver event
  - Thorough follow-up of the liver event should include
- These investigations can include based on investigator's discretion: serology tests, imaging and pathology assessments, hepatologist's consultancy; obtaining more detailed history of symptoms and prior or concurrent diseases, history of concomitant drug use, exclusion of underlying liver disease.

All follow-up information and procedures performed must be recorded as appropriate in the CRF.

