## 16.3 Appendix 3: Liver event and laboratory trigger definitions & follow-up requirements

**Table 16-1 Liver event and laboratory trigger definitions**

	Definition/ threshold
Liver laboratory triggers If ALT, AST and total bilirubin normal at baseline:	

• ALT or AST <math>> 5 \times</math> ULN

• ALP <math>> 2 \times</math> ULN (in the absence of known bone pathology)

• Total bilirubin <math>> 3 \times</math> ULN (in the absence of known Gilbert syndrome)

• ALT or AST <math>> 3 \times</math> ULN and INR <math>> 1.5</math>

• Potential Hy's Law cases (defined as ALT or AST <math>> 3 \times</math> ULN and Total bilirubin <math>> 2 \times</math> ULN [mainly conjugated fraction] without notable increase in ALP to <math>> 2 \times</math> ULN)

• Any clinical event of jaundice (or equivalent term)

• ALT or AST <math>> 3 \times</math> ULN accompanied by (general) malaise, fatigue, abdominal pain, nausea, or vomiting, or rash with eosinophilia

• Any adverse event potentially indicative of a liver toxicity*

If ALT or AST abnormal at baseline:	

• ALT or AST <math>> 2 \times</math> baseline or <math>> 300</math> U/L (whichever occurs first)

\*These events cover the following: hepatic failure, fibrosis and cirrhosis, and other liver damage-related conditions; non-infectious hepatitis; benign, malignant and unspecified liver neoplasms ULN: upper limit of normal

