**Table 16-2 Follow up requirements for liver laboratory triggers with liver symptoms**

ALT	TBL	Liver Symptoms	Action
ALT increase without bilirubin increase:			
If normal at baseline: ALT > 3 x ULN	Normal For patients with Gilbert's syndrome: No change in baseline TBL	None	
 
Measure ALT, AST, ALP, GGT, TBIL, INR, albumin, CK, and GLDH in 48-72 hours.
 
Follow-up for symptoms.
 

If elevated at baseline: ALT > 2 x baseline or > 300 U/L (whichever occurs first)			
If normal at baseline: ALT > 5 x ULN for more than two weeks	Normal For patients with Gilbert's syndrome: No change in baseline TBL	None	
 
Measure ALT, AST, ALP, GGT, TBIL, INR, albumin, CK, and GLDH in 48-72 hours.
 
Follow-up for symptoms.
 

If elevated at baseline: ALT > 3 x baseline or > 300 U/L (whichever occurs first) for more than two weeks			
 
Initiate close monitoring and workup for competing etiologies.
 

If normal at baseline: ALT > 8 x ULN	Normal	None	
ALT increase with bilirubin increase:			
If normal at baseline: ALT > 3 x ULN	TBL > 2 x ULN (or INR > 1.5)	None	
If elevated at baseline: ALT > 2 x baseline or > 300 U/L (whichever occurs first)	For patients with Gilbert's syndrome: Doubling of direct bilirubin		
If normal at baseline: ALT > 3 x ULN	Normal or elevated	Severe fatigue, nausea, vomiting, right upper quadrant pain	
If elevated at baseline: ALT > 2 x baseline or > 300 U/L (whichever occurs first)			

Isolated elevation of AST >3 x ULN needs to be interpreted in context of the clinical picture and other liver parameters, and further investigated for non-liver related etiology.

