**Table 16-3 Follow up requirements for liver laboratory triggers**

Criteria	Actions required	Follow-up monitoring
Total Bilirubin (isolated)		
>1.5 – 3.0 ULN	Repeat LFTs within 48-72 hours	Monitor LFTs weekly until resolution c to ≤ Grade 1 or to baseline
> 3 - 10 × ULN (in the absence of known Gilbert syndrome)	Repeat LFT within 48-72 hours Hospitalize if clinically appropriate Establish causality Record the AE and contributing factors (e.g., conmeds, med hx, lab) in the appropriate CRF	Monitor LFTs weekly until resolution c to ≤ Grade 1 or to baseline (ALT, AST, total bilirubin, Alb, PT/INR, ALP and GGT) Test for hemolysis (e.g., reticulocytes, haptoglobin, unconjugated [indirect] bilirubin)
> 10 x ULN	Hospitalize the participant Establish causality Record the AE and contributing factors (e.g., conmeds, med hx, lab) in the appropriate CRF	ALT, AST, total bilirubin, Alb, PT/INR, ALP and GGT until resolution c (frequency at investigator discretion)
Any AE potentially indicative of a liver toxicity*	Hospitalization if clinically appropriate Establish causality Record the AE and contributing factors (e.g., conmeds, med hx, lab) in the appropriate CRF	Investigator discretion

aElevated ALT/AST > 3 × ULN and TBL > 2 × ULN but without notable increase in ALP to > 2 × ULN

b(General) malaise, fatigue, abdominal pain, nausea, or vomiting, or rash with eosinophilia

cResolution is defined as an outcome of one of the following: (1) return to baseline values, (2) stable values at three subsequent monitoring visits at least 2 weeks apart, (3) remain at elevated level after a maximum of 6 months, (4) liver transplantation, and (5) death.

Based on investigator's discretion investigation(s) for contributing factors for the liver event can include: Serology tests, imaging and pathology assessments, hepatologist's consultancy; obtaining more detailed history of symptoms and prior or concurrent diseases, history of concomitant drug use, exclusion of underlying liver disease.

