2.8.3 Laboratory data

Laboratory data include measurements of all parameters below:

Test Category	Test Name
Hematology	Hematocrit, Hemoglobin, Platelets, Red blood cells, White blood cells, Differential (Basophils, Eosinophils, Lymphocytes, Monocytes, Neutrophils, Other)
Chemistry	Albumin, Alkaline phosphatase, ALT, AST, Gamma-glutamyl-transferase (GGT), Lactate dehydrogenase (LDH), Bicarbonate, Calcium, Magnesium, Phosphorus, Chloride, Sodium, Potassium, Creatinine, Creatine kinase, Direct Bilirubin, Total Bilirubin, Total Protein, Blood Urea Nitrogen (BUN) or Urea, Uric Acid, Amylase, Lipase, Glucose (non-fasting), CRP, D-Dimer, Ferritin
Coagulation	Prothrombin time (PT), International normalized ratio [INR], Activated partial thromboplastin time (APTT)
Pregnancy Test	Serum / Urine pregnancy test

Clinically notable abnormalities and abnormalities in liver function tests (LFT) are described in [Section 5.5](#).

Absolute values and change from baseline will be summarized for continuous laboratory parameters by treatment and scheduled visit, including the worst post-baseline value. The direction of interest for worst post-baseline value for selected hematology and biochemistry parameters is shown in [Section 5.4](#).

For selected laboratory tests, the number and percentage of patients with newly occurring or worsening laboratory abnormalities meeting the clinically notable criteria at any time post-

baseline, considering all post-baseline data from scheduled, unscheduled and premature discontinuation visits, will be summarized by treatment and laboratory parameter.

Furthermore, the number and percentage of patients with newly occurring or worsening abnormalities in liver function tests (LFT) will be summarized by treatment and at any time post-baseline considering all post-baseline data from scheduled, unscheduled and premature discontinuation visit.

The number (%) of patients with newly occurring or worsening of notable laboratory values will be provided.

Shift tables using the low/normal/high/ (low and high) classification will be used to compare baseline to the worst post-baseline value.

Listing of all laboratory data of patients with notable abnormal laboratory values will be provided with the classifications relative to the laboratory normal ranges.

Urine pregnancy test data will be summarized using frequency and percentage by treatment. A listing of all pregnancy test data will be provided.

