When a criterion contains multiple laboratory parameters, the criterion will only be considered to have been met when all conditions occur within a 3-day window. A case where all criteria are met at a post-baseline time point will be considered as newly occurring if the criteria are not met at baseline and will be considered as worsening if the criteria are met at baseline and at least one component is worsening from baseline irrespective of whether the other(s) are better.

Table 5.5-2 Notable liver function test values

Criterion
ALT > 3 x the upper limit of normal range (ULN)
ALT > 5 x ULN
ALT > 8 x ULN
ALT > 10 x ULN
ALT > 20 x ULN
ALT or AST > 3 x ULN
ALT or AST > 5 x ULN
ALT or AST > 8 x ULN
ALT or AST > 10 x ULN
ALT or AST > 20 x ULN
Total bilirubin > 1 x ULN
Total bilirubin > 1.5 x ULN
Total bilirubin > 2 x ULN
Total bilirubin > 3 x ULN
ALP > 1.5 x ULN
ALP > 2 x ULN
ALP > 3 x ULN
ALP > 5 x ULN
ALT or AST > 3 x ULN and total bilirubin > 1.5 x ULN
ALT or AST > 3 x ULN and total bilirubin > 2 x ULN
ALT or AST > 5 x ULN and total bilirubin > 2 x ULN
ALT or AST > 8 x ULN and total bilirubin > 2 x ULN
ALT or AST > 10 x ULN and total bilirubin > 2 x ULN
ALT or AST > 20 x ULN and total bilirubin > 2 x ULN
ALT > 3 x ULN and total bilirubin > 2 x ULN
ALP > 5 x ULN and total bilirubin > 2 x ULN
ALT or AST > 3 x ULN and Total Bilirubin > 2 x ULN and ALP < 2 x ULN (Hy's law)

ALT = alanine aminotransferase, AST = aspartate aminotransferase, ALP = alkaline phosphatase

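### The SAP's 3-day rule leaves out of every combined ALT/AST-bilirubin row, including Hy's law, a patient whose bilirubin first rises more than 3 days after the last raised ALT or AST

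*SAP*

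**What the plan says.** SAP 5.5 sets the timing rule for liver criteria with more than one laboratory parameter: "the criterion will only be considered to have been met when all conditions occur within a 3-day window". Table 5.5-2 has nine such rows. Eight pair ALT or AST with total bilirubin, and one pairs ALP with total bilirubin. The Hy's law row reads "ALT or AST > 3 x ULN and Total Bilirubin > 2 x ULN and ALP < 2 x ULN (Hy's law".

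SAP 2.8.3 counts new or worsening liver test abnormalities "at any time post-baseline considering all post-baseline data from scheduled, unscheduled and premature discontinuation visit", so unscheduled samples are eligible.

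Protocol Table 16-1 lists potential Hy's "Law cases (defined as ALT or AST" above 3 x ULN, with total bilirubin above 2 x ULN and no notable ALP rise above 2 x ULN. It gives no time limit between the components.

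The protocol also calls for repeat testing. After ALT above 3 x ULN with normal bilirubin and no symptoms, Table 16-2 says "Measure ALT, AST, ALP, GGT, TBIL, INR, albumin, CK, and GLDH in 48-72 hours". After an isolated bilirubin rise, Table 16-3 asks for a repeat in 48-72 hours and then "Monitor LFTs weekly until resolution". Protocol 10.2.1 adds: "If the initial elevation is confirmed, close observation of the patient will be initiated".

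**The concern.** The combined rows are the SAP's tabulated laboratory screen for serious drug-related liver injury. In a sequential pattern, ALT or AST rises first and bilirubin follows, possibly after the enzymes have come down. A short coincidence window removes such a patient from the combined counts when the second rise comes late enough. The SAP gives no reason for the window, and the protocol definition that bears the same name has none. At stake is whether the by-arm liver tables can show such a case as one linked event.

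**Working it through.** No figure in the plan needs reproducing. The check is on dates.

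**1. What the rule excludes.** For a given row, let tA be the last day with ALT or AST above that row's limit, and tB the first day with bilirubin above its limit, with tB later than tA. Every pair of one raised-enzyme sample and one raised-bilirubin sample is then at least tB - tA days apart. If tB - tA > 3, no pair meets the rule. More frequent sampling locates tA and tB better but cannot close a true gap longer than 3 days.

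**2. Which rows are affected.** The lowest bilirubin limit in the eight ALT/AST-bilirubin rows is 1.5 x ULN and the lowest enzyme limit is 3 x ULN. If bilirubin first exceeds 1.5 x ULN more than 3 days after the last ALT or AST above 3 x ULN, all eight rows are missed. If it passed 1.5 x ULN in time but 2 x ULN too late, the patient may enter the 1.5 x ULN row but still misses Hy's law. The ninth row (ALP with bilirubin) does not involve ALT or AST and does not recover the case.

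**3. What the repeat panel recovers.** 48 and 72 hours are 48/24 = 2 and 72/24 = 3 days. If the window means a date difference of at most 3, both fall inside. ALT above 3 x ULN at one draw and bilirubin above 2 x ULN at that repeat then count, even if ALT has fallen in between, as long as the row's ALP condition also holds in the window. The SAP does not define the window's edges. Under its duration convention in 2.1.1.3 (end - start + 1), the same repeats span 3 and 4 days, and the 72-hour one falls outside.

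**4. An illustration (assumed values).** ALT is 6 x ULN on Day 15. The repeat on Day 17 or 18 shows bilirubin below every limit. On Day 29 bilirubin is first raised, at 2.5 x ULN, with ALT at 2.5 x ULN.
- If ALT and AST were at or below 3 x ULN from Day 26 on, the last enzyme elevation is Day 25 at the latest. Then 29 - 25 = 4 > 3, and no combined row counts the patient.
- If ALT instead fell in a straight line, the slope is (6 - 2.5)/(29 - 15) = 0.25 x ULN per day, and ALT reaches 3 x ULN on Day 15 + (6 - 3)/0.25 = Day 27. A sample on Day 26 would read 6 - 0.25 x 11 = 3.25 x ULN, and 29 - 26 = 3, so with that sample the patient could be counted.

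The outcome depends on the true separation, and within 3 days on whether a sample was taken.

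**5. Where the missed patient still shows.** If these limits were not met at baseline, the patient enters the single-parameter rows for ALT > 3 and > 5, ALT or AST > 3 and > 5, and bilirubin > 1, > 1.5 and > 2 (all x ULN). SAP 2.8.3 lists all laboratory data of patients with notable values. ALT of 6 x ULN also meets a Table 16-1 trigger (ALT or AST > 5 x ULN, if normal at baseline), so the case can be a liver AESI. SAP 2.8.1.1 analyses AESIs as the investigator flags them. None of these outputs counts, by arm, patients with both elevations in sequence.

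**The case against.** The strongest reply is that follow-up is active. A raised ALT leads to a repeat panel inside or at the edge of the window, confirmed elevations are closely observed, and unscheduled results are used. This stands for rises within about 3 days. It does not reach later ones.

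A second reply is that Table 16-1 is a trigger for site follow-up, so its silence on timing does not mean any time over 91 days. This also stands: the two documents differ but do not contradict each other. The reason to change is what the table can detect.

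A third is that any-time pairing may join unrelated events, such as an early enzyme rise from acute COVID-19 and a much later bilirubin rise. This is fair, and is why the 3-day rows should stay and the added pairs need medical review.

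A reader might infer that sparse blood sampling causes the loss. In Part A the row "Hematology, chemistry and coagulation safety tests" of Protocol Table 8-1 places draws at Days 1 (pre-dose), 3, 15, 29, 61 and 91. The gaps after Day 3 are 12, 14, 32 and 30 days, and the smallest allowed by the visit windows is (29 - 5) - (15 + 3) = 6 days. On scheduled draws alone the rule does reduce to a single-sample rule. But unscheduled results count too, and for a separation over 3 days the rule excludes the case under any schedule. The spacing is not the cause.

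**Conclusion.** The point holds in a limited form. The 3-day rule removes late sequential cases from all eight ALT/AST-bilirubin rows, including Hy's law, and no other planned laboratory table counts them by arm. It is a cheap improvement to the safety outputs. No efficacy result is affected.

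Three stronger readings are not supported. Not every case in which bilirubin rises after ALT has fallen is lost, because a rise caught at the repeat panel can count. The patient-level link is not lost, because the listing keeps it. Nor can one say that a missed case would remove the whole signal: the documents give no liver event rates, so neither the expected number of combined cases nor the share missed can be calculated.

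The conclusion assumes that the rule is programmed as written and that the window is a date difference of at most 3 days. An inclusive day count would exclude slightly more. The rule is not limited to one Part, but the draw days checked here are those of Part A.

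**What to change.** In SAP 5.5, keep the 3-day rows, state how the window is counted, and add by arm:

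- **Sequential rows.** For the ALT/AST-bilirubin criteria, count a patient when bilirubin exceeds its limit on or after the first post-baseline ALT/AST elevation, at any later time. For Hy's law, judge ALP at the time of the ALT/AST elevation and not at its overall peak; otherwise a later unrelated ALP rise would remove a real case. State how the new-or-worsening rule applies to these rows.
- **A scatter plot.** Show each patient's peak post-baseline ALT or AST against peak total bilirubin, by arm, in multiples of ULN.

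The cost is SAP wording, one table or plot, and medical review of a few possibly unrelated pairs. No new samples or visits are needed.

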5.6 Vital signs – definition of clinically notable values

Table 5.6-1 shows the clinical notable criteria for vital signs.

Table 5.6-1 Clinical notable criteria for vital signs

Vital sign	Direction	Patient age at screening	
		< 18 years	≥ 18 years
Systolic blood pressure [mmHg]	High	≥ 95th percentile of the age and height group1	≥ 180 with increase from baseline of ≥20 mmHg
	Low	≤ 5th percentile of the age and height group1	≤ 90 with decrease from baseline of ≥20 mmHg
Diastolic blood pressure [mmHg]	High	≥ 95th percentile of the age and height group1	≥ 105 with increase from baseline of ≥15 mmHg
	Low	≤ 5th percentile of the age and height group1	≤ 50 with decrease from baseline of ≥15 mmHg
	High	≥ 38.4°C	≥ 39.1°C

Vital sign	Direction	Patient age at screening	
		< 18 years	≥ 18 years
Oral body temperature [°C]	Low	≤ 35.0°C	
Pulse rate [bpm] 2	High	1-6 months	> 160
		6-12 months	> 150
		12-18 months	> 140
		18-24 months	> 135
		2-3 years	> 128
		3-4 years	> 123
		4-6 years	> 117
		6-8 years	> 111
		8-12 years	> 103
		12-15 years	> 96
Pulse rate [bpm] 2	Low	≥ 15 years	> 92
		1-6 months	< 120
		6-12 months	< 110
		12-18 months	< 103
		18-24 months	< 98
		2-3 years	< 92
		3-4 years	< 86
		4-6 years	< 81
		6-8 years	< 74
		8-12 years	< 67
Weight	High	increase from baseline ³ of ≥ 2 BMI- for-age percentile categories ⁴	
	Low	decrease from baseline ³ of ≥ 2 BMI- for-age percentile categories ⁴	
Respiratory rate [breath per minute] ^{2,6,7}	High	1-6 months	> 55
		6-12 months	> 50
		12-18 months	> 46
		18-24 months	> 40
		2-3 years	> 34
		3-4 years	> 29
		4-6 years	> 27
		6-8 years	> 24
		8-12 years	> 22
		12-15 years	> 21
		≥ 15 years	> 20
	Low	1-6 months	< 33
		6-12 months	< 30

Vital sign	Direction	Patient age at screening	
		< 18 years	≥ 18 years
12-18 months	<28		
18-24 months	< 25		
2-3 years	< 22		
3-4 years	< 21		
4-6 years	< 20		
6-8 years	< 18		
8-12 years	< 16		
12-15 years	< 15		
≥ 15 years	< 13		

Oxygen saturation Low <=93%

bpm=beats per minute; NHLBI= National Heart, Lung, and Blood Institute;

1 Blood pressure percentiles are calculated for each blood BP record using the method described in Appendix B of the following reference: The Fourth Report on Diagnosis, Evaluation and Treatment of High Blood Pressure in Children and Adolescents. Pediatrics 2004; 114; 555.

5.7 Statistical models

5.7.1 Primary analysis

The following ANCOVA will be used for time-weighted change from baseline in \log_{10} SARS-CoV-2 viral load through Day 8:

Dependent variable = intercept + treatment + baseline in \log_{10} SARS-CoV-2 viral load + baseline risk for COVID-19 disease progression + presence of SARS-CoV-2 antibodies at baseline + geographic region + error.

The SAS procedure PROC MIXED will be used for analysis. Results will be presented with LSM and standard error (SE) for treatment effects and LSM, SE, associated two-sided 95% confidence interval, and two-sided p-value for treatment contrasts of each ensovibep dose versus Placebo.

- **MCP-Mod**

The Multiple Comparison Procedure – Modelling (MCP-Mod) methodology (see [Bretz et al 2005](#) and [Pinheiro et al 2014](#)) will be employed to assess the primary objective. The following steps for the MCP-Mod methodology will be performed. The analysis will be implemented in SAS (used for ANCOVA) and R (MCP-Mod) using DoseFinding R package:

Step 1 (Testing an overall dose-response signal - MCP part):

- a. Fit ANCOVA model. Extract estimates and variance-covariance matrix from fitted model.
- b. Perform multiple contrast test with pre-defined model types and optimal contrasts, using variance-covariance matrix from the ANCOVA.

Consider the following candidate models:

- Emax (ED50=8)
- Emax (ED50=40)
- Emax (ED50=180)
- sigEmax (ED50=120, h=4)
- sigEmax (ED50=450, h=3)

Present t-statistics and corresponding adjusted p-values for each candidate model.

If there is at least one significant DR relationship, the DR signal is declared and Step 2 will be performed.

Step 2 (Estimation of the dose-response curve and target dose – Mod part):

- a. Draw bootstrap samples (at least 1000) from a multivariate normal distributions $N(\mu, \sigma)$ with parameter μ and σ populated with the corresponding LSMeans and variance-covariance from the ANCOVA of step 1a. Fit each of the pre-defined models to the data of each sample. Select the model with the best fit based on generalized AIC and predict the dose-response curve with this model in each sample.
- b. Derive median and other quantiles for predicted response over the dose range from the bootstrap samples. This will result in an averaged model.
- c. Estimate the target dose(s) for a delta of 0.3, 0.8, and 1.5 using inverse regression techniques using the best model for each of the bootstrap samples. If at least 50% of the target doses are within the investigated dose range the target dose will be derived as the median of the bootstrap samples, the 95% interval will be derived from the respective quantiles. For this derivation only target doses within the boundaries for the parameter are included (i.e. range of 0 – 1.5*maxdose for Emax and sigEmax, 0 – 2*maxdose for exponential).

• Multiple imputation for supplementary analysis

A treatment policy will be used to handle (1) post-treatment initiation of all antivirals (including convalescent serum, antiviral antibodies, and antiviral small molecules) and immunosuppressive medications; and, (2) post-treatment increase in dose of immunosuppressive medications, for the treatment or management of COVID-19, and a patient will be evaluated regardless of experiencing either of these intercurrent events.

A composite strategy will be used to handle (3) death from any cause and (4) COVID-19 related hospitalization. In the event a patient experiences death or COVID-19 related hospitalization, all values after the time of death/start of COVID-19 related hospitalization for change from

baseline in \log_{10} SARS-CoV-2 viral load will be set as the worst observed value based on observed values at each time point within each treatment arm independently.

All measurements in \log_{10} SARS-CoV-2 viral load missing for other reason than death or COVID-19 related hospitalization will be multiply imputed assuming patients in the ensovibep treatment arms behave as patients in the placebo arm, i.e. using jump-to-reference (J2R). Missing data of patients in the placebo treatment arm will be imputed using missing at random (MAR) assumption.

For supplemental analysis using multiple imputation the following imputation steps need to be performed for missing data.

Missing data will be imputed for the visits before deriving the time-weighted change from baseline. Imputations will be done for change from baseline \log_{10} SARS-CoV-2 viral load, not for the absolute value:

1. Impute missing data using MAR for patient in the placebo arm:

Select all patients from the placebo arm, impute missing values at Day 3, 5 and 8 using the MI approach based on the fully conditional specification (FCS) method for 100 time and obtain 100 imputed datasets. Missing Day 3 values will be imputed using a model with the imputed values of baseline risk of COVID-19 progression, baseline in \log_{10} SARS-CoV-2 viral load, presence of SARS-CoV-2 antibodies at baseline and geographic region as predictors. Missing Day 5 values will be imputed using a model with the values of Day 3, baseline risk of progression, baseline in \log_{10} SARS-CoV-2 viral load presence of SARS-CoV-2 antibodies at baseline and geographic region as predictors. Repeat the same for subsequent visits.

This results in at least 100 imputed datasets.

2. Impute missing for patients in the ensovibep treatment groups using J2R:

Select all patients, impute missing values at Day 3, 5 and 8 using the MI approach, under assumption of missing not at random (MNAR) that patients in ensovibep treatment groups will behave as patients treated with Placebo, based on the fully conditional specification (FCS) method for 100 time and obtain 100 imputed datasets. Missing Day 3 values will be imputed using a model with the imputed values of baseline risk of COVID-19 progression, baseline in \log_{10} SARS-CoV-2 viral load, presence of SARS-CoV-2 antibodies at baseline and geographic region as predictors. Missing Day 5 values will be imputed using a model with the values of Day 3, baseline risk of progression, baseline in \log_{10} SARS-CoV-2 viral load presence of SARS-CoV-2 antibodies at baseline and geographic region as predictors. Repeat the same for subsequent visits.

This results in 100 imputed datasets.

3. Set datasets from step 1 and step 2.
4. Derive time weighted change from baseline for each patient and each imputed dataset.
5. Data of the final multiply-imputed dataset where all missing values are filled will be analyzed (by imputed dataset) using the ANCOVA as specified for the primary analysis.
6. The results for the treatment effect from at least 100 datasets will then be combined using Rubin's rule.

Step 1 to 6 will be implemented before MCP-Mod is used.

Step 5 and 6 will be used within MCP-Mod for step 1a Step 1b and 2a of the MCP-Mod will use the combined estimate and variance-covariance matrix of step 6.

- **Repeated measures ANCOVA (MMRM) for supportive analyses**

The following repeated measure ANCOVA (MMRM) will be used for change from baseline in \log_{10} SARS-CoV-2 viral load:

Dependent variable = intercept + treatment + baseline \log_{10} SARS-CoV-2 viral load + baseline risk for COVID-19 disease progression + presence of SARS-CoV-2 antibodies at baseline + geographic region + visit + treatment*visit + baseline \log_{10} SARS-CoV-2 viral load *visit + error.

The within-patient correlation will be modeled using an unstructured covariance matrix in the mixed model. The Kenward-Roger approximation will be used to estimate denominator degrees of freedom ([Kenward and Roger 1997](#)).

If the model fails to converge with unstructured covariance matrix, either a compound symmetry (first choice) or first order autoregressive (AR1) (second choice) covariance structure will be used.

The SAS procedure PROC MIXED will be used for analysis. Results will be presented with LSM and standard error (SE) for treatment effects and LSM, SE, associated two-sided 95% confidence interval, and two-sided p-value for treatment contrasts of each ensovibep dose versus placebo.

Handling of intercurrent events follows the primary analysis. Any missing data for other reason than death/COVID-29 related hospitalization are considered MAR and handled as such in the MMRM.

